**2. Quality Comparators (Outcomes for Aim 2 and exposures for Aims 3 and 4)**

Each quality comparator is made up of patient or proxy answers to several questions rated either as: "very satisfied, satisfied, dissatisfied, or very dissatisfied" or as: "strongly agree, agree, disagree, or strongly disagree" during the patient's baseline interview. Higher values will be coded to represent negative connotations. The comparators and component questions address: **Comparator 1: Care Coordination and Quality:** 5 questions on overall quality of care, information given, follow-up care, concern for overall health, and needs met at same location. **Comparator 2: Access Barriers:** 3 questions on availability of night/weekend, ease/convenience, and out-of-pocket costs. **Comparator 3: Technical Skills of PCP:** 3 questions about checking "everything", understanding medical history, and understanding what is wrong. **Comparator 4: Interpersonal Skills of PCP:** 4 questions about whether or not the PCP is in a hurry, does not explain, does not discuss, and acts like doing a favor. **Comparator 5: Quality of Information provided by PCP:** 4 questions about whether the PCP "tells all I

PRINCIPAL INVESTIGATOR (LAST, FIRST, MIDDLE): [name]

want to know,” “answers all my questions,” “has my confidence,” and dependence on doctor(s) to “feel better both physically and emotionally.” Combination of these questions into 5 comparator measures is supported by factor analyses with factor loadings of items on the 5 scores of 0.55 or greater. Cronbach’s coefficient alpha was 0.82 for global quality, 0.54 for access barriers, 0.89 for PCP technical skills, 0.79 for interpersonal manner, and 0.84 for Information giving. Average item-level responses will be determined for each variable. Comparators 1 and 2 will be available for all patients, but PCP comparators only for the approximately 90% of patients who have regular PCPs. Comparators will be presented trichotomously, addressing high and low quality extremes. For the access and quality comparators, the best and worse access and quality will be compared to the middle quartiles. For the PCP comparators, no PCP and quality in the highest quartile will be compared to the 3 lower quartiles similar to the approach taken by Lee and Casper.

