#### Data Analysis

Complex survey design: The MCBS uses a multi-stage clustering sample with unequal sampling probabilities. We will take into account the complex design by using appropriate survey commands in Stata to calculate the correct point estimates and their variances. Specifically, the set of longitudinal weights (RIC X2) allowing analysis of data trends over a two year period and a second set of longitudinal weights (RIC X3) will be applied to two- and three-year outcomes.

Proxies: Proxy responses will be included in all models. About 9.8% of MCBS baseline interviews were conducted by proxies and our previous work indicates that exclusion of proxy responses results in underestimates of disability prevalence. Recognizing this may explain proxy differences we will explore replacing proxy status with reason for proxy use.

Missing data and attrition: See Avoidance of Bias below.

General approach to analysis: Each Aim will describe the sample of Medicare beneficiaries with weighted uni-variable summary statistics appropriate to the distributional characteristics of the variables of interest and bi-variable associations with outcomes. Because of concerns that some variables may be intermediate on causal pathways, to understand associations, we will build etiological models hierarchically. All will control for baseline age, gender, race, ADL or

PRINCIPAL INVESTIGATOR (LAST, FIRST, MIDDLE): [name]

IADL stage, and proxy status. Health conditions and living circumstances will be added sequentially, selected according to associations with functional change, institutionalization, or mortality or according to emergent themes from stakeholder groups. The Goodness-of-Fit (GOF), Deviance and Pearson GOF Statistic, ROC curve, and r-square values as appropriate to each regression will be reported to document model fit of the multinomial regressions. Stata 11.0 (Stata Corp, College Station, Texas) will be used for all analyses (except for multiple imputation as noted below). A 2-sided  $p<.05$  will be used for all final tests of significance.

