#### Sample size

We did power calculation for Aims 2 and 3. Here, we focus on the association between ADL stage and the first comparator, care coordination and quality, in Aim 2, and that between the first comparator and transition in Aim 3.

First, we show the detectable RRRs for associations between ADL stages and the first comparator. Using our preliminary data in Table 2 which included three panels, we assume the distribution of the ADL stages will be similar across 10 years for which we will request the data for the project. After trichotomizing the first comparator, we obtained the proportion for the three categories (1, 2, and 3 from dissatisfied to satisfied) for stage I. They are 13.32%, 60.19%, and 26.49%.

Relative risk of being dissatisfied is defined as the probability of being dissatisfied divided by the probability of being neither dissatisfied nor satisfied. The detectable RRRs comparing other stages to stage I are shown in Table 3. With 10 years of data, we will be able to detect RRRs of 0.91 and 1.07 when comparing stages 0 to I. The RRRs we observed using 1 year data are actually much bigger than these, which indicate that we have adequate power.

Table 3. Detectable RRRs comparing other Stages to Stage I (assuming 80% power and 5% significance level)

	Category 1 versus Category 2	Category 3 versus Category 2
Stage 0 versus I	0.91	1.07
Stage II versus I	1.15	0.89
Stage III versus I	1.16	0.88
Stage IV versus I	1.29	0.80

We then calculate the detectable RRRs when we compare the transition outcome across the three groups for the first comparator. We again assume the distribution of the first comparator will be similar across 10 years and the transition probability for the reference category, "neither dissatisfied nor satisfied," was estimated from the 1 year transition in ADL stages for the three panels that were active in both 2005 and 2006. Relative risk of functional improvement is defined as the probability of ADL functional improvement divided by the probability of being stable in ADL stage. All the detectable risk ratios (Table 4) are smaller than 2 except for one RRR for institutionalization, which indicate ample power for our analysis.

Table 4. Detectable RRRs of transition (functional stable is the reference) for the three categories of the first comparator (assuming 80% power and 5% significance level)

	Death	Institutionalization	Functional deterioration	Functional improvement

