Dissatisfied vs. neither dissatisfied nor satisfied	1.71	2.71	1.50	1.49
Satisfied vs. neither dissatisfied nor satisfied	1.24	1.63	1.16	0.90

Qualitative: The SL group analyses will include geographically diverse stakeholders with a variety of socioeconomic circumstances, disabilities, comorbidities, and life circumstances. The SL groups will be computer literate. The addition of Urban groups further enriches the sample

PRINCIPAL INVESTIGATOR (LAST, FIRST, MIDDLE): [name]

by obtaining PWD from a predominantly minority low literacy population. The SL and Urban recruitment strategies enable the inclusion of hard-to-reach people, including those who face numerous disability-related, economic, educational, social class, ethnicity, and cultural barriers.

By design, the MCBS samples are weighted to be representative of the entire elderly and working age Medicare population, and thus by its nature will include a diverse study population. The sample will also have a wide range of medical comorbidities. Preliminary results (Table 5) show diversity with respect to ADL and IADL stage as well as transition outcome status (above). Finally, the sampling frame is designed to be geographically diverse. Table 5 provides sample size estimates from 3 active panels of respondents at the fall 2006 Access to Care interview (about 3/10ths the study sample size). Over 4 and 5 million people had mild ADL or IADL limitations, respectively, with another 4.6 and 7.0 million people having more serious ADL and IADL limitations. Between-group differences across the 5 comparators will be addressed quantitatively according to the transition outcomes with independent effects of ADL and IADL stage determined.

Table 5. Sample size shown for 3 panels; expected size for 10 panels will be 40,000

Stage	Difficulties in ADL			Difficulties in IADL		
	Raw N	Expected N in population (million)	Weighted percent (SE on weighted %)	Raw N	Expected n in population (million)	Weighted percent (SE on weighted %)
0	8208	21.1	69.25 (0.86)	6924	18.2	59.65 (0.97)
I	1942	4.8	15.73 (0.50)	2094	5.3	17.5 (0.59)
II	995	2.4	7.72 (0.37)	1141	2.9	9.45 (0.37)
II	728	1.8	5.97 (0.36)	1558	3.4	11.1 (0.41)
IV	185	0.4	1.33 (0.14)	341	0.7	2.3 (0.15)
Total	12058	30.5	100	12058	30.5	100

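### Table 4's detectable RRRs do not follow from the comparator split behind Table 3 or from the planned quartile cut, if both rows use one N and method

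*Combined protocol and SAP*

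**What the plan says.** The section on quality comparators averages item responses for each comparator. For comparators 1 and 2 it then forms three groups: "the best and worse access and quality will be compared to the middle quartiles". Read plainly, that is a nominal 25/50/25 cut. The satisfaction items have four response options ("very satisfied, satisfied, dissatisfied, or very dissatisfied") and no neutral one. No cut-off value on the averaged score is printed.

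The Sample size section uses comparator 1 for both power tables. For Table 3 (Aim 2) it gives proportions "for the three categories (1, 2, and 3 from dissatisfied to satisfied) for stage I": "They are 13.32%, 60.19%, and 26.49" (per cent). For Table 4 (Aim 3) it prints neither the group shares nor the reference transition probabilities. It says only that the comparator's distribution is taken to be similar over the ten years and that the reference transitions come from the 2005 to 2006 panels. Both tables carry the note "assuming 80% power and 5% significance level". The Data Analysis section makes tests two-sided at .05.

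Table 4, whose first row is labelled "Dissatisfied vs. neither dissatisfied nor satisfied", reads:

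| | Death | Institutionalization | Deterioration | Improvement |
|---|---|---|---|---|
| Dissatisfied vs. middle | 1.71 | 2.71 | 1.50 | 1.49 |
| Satisfied vs. middle | 1.24 | 1.63 | 1.16 | 0.90 |

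The section concludes: "All the detectable risk ratios (Table 4) are smaller than 2 except for one RRR for institutionalization, which indicate ample power for our analysis".

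**The concern.** The two rows of Table 4 lie much further apart than the group sizes elsewhere in the plan allow. A quartile cut makes the outer groups equal, so their detectable RRRs in the same direction should be equal. Under Table 3's split they should differ modestly.

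The improvement column is also odd against its neighbour. Its dissatisfied entry almost equals that for deterioration (1.49 and 1.50), which suggests similar transition probabilities. Its satisfied entry does not match: |ln 0.90| = 0.105 against ln 1.16 = 0.148.

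Table 4 is the plan's only statement of what Aim 3 can detect, and the claim of ample power rests on it. If it does not describe the planned comparator, a reader cannot tell which effects on death, institutionalization or function the study could miss. The same trichotomy is the exposure in Aim 3 and feeds the Aim 4 simulations and the surveillance tool.

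**Working it through.** **Inputs from the plan.** 80% power; two-sided 5%; stage I split 13.32/60.19/26.49; nominal quartiles 25/50/25; the entries of Tables 3 and 4; Table 5 stage counts 8208, 1942, 995, 728 and 185 (total 12,058); expected N 40,000; preliminary N 10,399.

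**Assumed.** The probability of a stable stage in the reference group is not printed. I used 0.70 and varied it from 0.5 to 0.8.

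**Formula.** The detectable RRR solves |ln RRR| = (1.960 + 0.842) × SE. SE² is the sum of 1/(expected count) over four cells: outcome and reference category, in each of two groups.

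**1. Table 3 as a check on the method.** With the printed split and Table 5's raw stage shares, N = 40,000 gives:
- category 1: 0.89, 1.19, 1.21, 1.39 (printed 0.91, 1.15, 1.16, 1.29);
- category 3: 1.09, 0.87, 0.85, 0.75 (printed 1.07, 0.89, 0.88, 0.80).

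An N of about 66,000 fits all eight cells to within about 0.005. If the dissatisfied share is also left free, the best fit is 13.5%. So Table 3 does rest on the 13.32% split, whatever N was used.

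**2. Log ratios printed in Table 4.**
- Death: ln 1.71 / ln 1.24 = 0.536/0.215 = 2.5
- Institutionalization: 0.997/0.489 = 2.0
- Deterioration: 0.405/0.148 = 2.7
- Improvement: 0.399/0.105 = 3.8

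**3. Log ratios expected from the group sizes.** For modest effects, SE² is proportional to 1/w(middle) + 1/w(outer), where w is the group share. N and any common design effect cancel, and the transition probability nearly cancels.
- Quartiles: both outer groups are 25%, so the ratio is 1.0.
- Table 3 split: √[(1/0.6019 + 1/0.1332) / (1/0.6019 + 1/0.2649)] = √(9.169/5.436) = 1.30.

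**4. Full calculation for death (N = 40,000, Table 3 split).** The groups are 24,076 middle, 10,596 satisfied and 5,328 dissatisfied. A reference death probability of 0.0207 returns the printed satisfied entry: cells 498.4, 16,853, 270.6 and 7,380.5; SE 0.0768; 2.802 × 0.0768 = 0.215; RRR 1.24. With the same probability, the dissatisfied group at RRR 1.31 has cells 498.4, 16,853, 143.6 and 3,705.8; SE 0.0964; 2.802 × 0.0964 = 0.270; RRR 1.31. The table prints 1.71.

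**5. Dissatisfied row predicted from the satisfied row.**

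| | Death | Institutionalization | Deterioration | Improvement |
|---|---|---|---|---|
| Printed | 1.71 | 2.71 | 1.50 | 1.49 |
| 13.32/60.19/26.49 | 1.31 | 1.81 | 1.21 | 1.14 |
| 25/50/25 | 1.24 | 1.63 | 1.16 | 1.11 |

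The first three columns hold to within rounding for N = 10,399, 40,000 and 66,000 and for stable probabilities 0.5 to 0.8, wherever a solution exists. The improvement entry of 0.90 has no solution at N = 10,399.

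**6. The reverse reading.** If the dissatisfied row is right, the same formula with Table 3's split puts the satisfied row at about 1.55, 2.35 and 1.39. With quartiles it would be 1.71, 2.71 and 1.50, because the outer groups are equal.

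**7. A different N in each row.** Keep the Table 3 split, with 40,000 behind the satisfied row. Using 10,399 behind the dissatisfied row gives 1.63, 2.75, 1.42 and 1.28; using 12,058 gives 1.58, 2.60 and 1.39 in the first three columns. These are closer, but neither reproduces the printed row.

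**The case against.** The strongest objection is that the row ratio is free of N only if both rows use the same N. Step 7 shows that mixing the 3-panel and 10-panel sizes removes much of the gap in three columns with no change of cut. That stands as a caution about the cause. It does not rescue the table, since no mix tried reproduces it and improvement stays far off.

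A reader might infer a third cut-off in the plan, with a very small dissatisfied group. Solving Table 4 for that share, with satisfied to middle at 26.49:60.19, gives about 2.5% (death), 3% (institutionalization), 2.2% (deterioration) and 1.0% (improvement), or 0.5 to 5.4% over all the assumptions tried. The documents do not support this reading. No section states such a share, and one cut cannot have several sizes. Stage I alone supplies 0.1332 × 15.73% = 2.1% of the whole sample. If stages II to IV are at least as dissatisfied, which is the direction of Table 3, the floor is 0.1332 × (100 − 69.25)% = 4.1%. An error in Table 4 is at least as likely.

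A reader might also take 13.32% as contradicting the quartile rule. The figure is for stage I only, while the quartiles are presumably of the whole sample. A mean of five 4-point items is also heavily tied, so a quartile rule need not give 25%. The mismatch is unexplained, but it does not prove a conflict.

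Finally, the data come from an existing survey, so Table 4 sets no recruitment target. Aim 2 also models the comparators continuously, and variable definitions are a scheduled deliverable. This limits the consequence, but leaves a stated power result that the plan's own inputs do not give.

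**Conclusion.** The point holds as an internal inconsistency in Table 4. On one N and one method, its rows cannot come from Table 3's split or from nominal quartiles. The log-RRR ratios are 2.0 to 3.8, where about 1.3 or 1.0 is expected.

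If the satisfied row is right, the dissatisfied row is too pessimistic: 1.71, 2.71 and 1.50 should be about 1.31, 1.81 and 1.21, or 1.24, 1.63 and 1.16. No entry would then exceed 2. If the dissatisfied row is right, the satisfied row is too favourable and both institutionalization entries exceed 2. Either way, the sentence about a single RRR above 2 does not survive. The improvement column fails under both splits and disagrees with the other columns.

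This rests on a Wald calculation for the log RRR and an assumed stable probability, which has almost no influence. Which row is wrong, and whether through the cut, the N or the arithmetic, cannot be settled from the documents.

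**What to change.** In the Sample size section, apply to comparator 1 the same trichotomization that the quality comparators section will use in the analysis. State beside the tables:

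- the realised whole-sample share of each group, as well as the stage I shares;
- the N behind each table;
- the reference-group transition probabilities from the 2005 to 2006 panels.

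Recompute Tables 3 and 4 from those inputs, including the 0.90 entry, and replace the sentence that counts RRRs above 2 with the recomputed values. If ties move the quartile groups away from 25%, say so there. The quartile approach itself need not change.

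The cost is a short text edit and a rerun of two power tables on data the team already holds. No new data are needed and the analysis is unchanged. The recomputed figures may be better or worse than those printed, depending on which row was at fault.

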#### Part D: Inclusiveness of Different Populations (Criterion 6)

The VAI and Urban groups clearly represent diverse populations of PWD as described above. Moreover the MCBS is by its nature diverse with respect to geographic location, age, gender, race/ethnicity, disabilities and comorbidities as sampled to reflect the Medicare population. These populations include many different sub-populations of people within them.

PRINCIPAL INVESTIGATOR (LAST, FIRST, MIDDLE): [name]

## REPLICATION AND REPRODUCIBILITY OF RESEARCH AND DATA SHARING PLAN

*(Use continuation pages as needed to provide the required information in the format shown below. Limit 2 pages for this section. Mouse over each underlined subheading for a short description of each. Refer to the PCORI [Application Guidelines](#) for additional information.)*

Provision of a complete, final study protocol, describing the study population; primary and secondary hypotheses to be tested; sources and methods of measuring exposures, outcomes, and all covariates used in analyses, including data definitions, coding instructions, discussion guides for qualitative research, and the analysis plan. The protocol will usually be expected to be delivered along with the first 12-month progress report, and always within three months of the end of the funding period. PCORI will reserve the right to share these materials with appropriate researchers, in consultation with the principal investigator of the study.

- Proposed clinical trials or observational outcomes studies must be registered at [www.clinicaltrials.gov](http://www.clinicaltrials.gov).
- Proposed evidence synthesis studies must be registered at <http://www.crd.york.ac.uk/prospero/>
- Descriptions of study datasets, including code books, meta-data related to the datasets, and documented programming code used for creating the final study population, for creating variables, and for conducting all outcomes analyses. These must be provided within three months of the end of the final funding year.

The project will encourage other research groups to replicate findings from this study in the MCBS and in other populations, such as veterans, as well as in other data sets. Work plans, variable definitions, methods applied, and findings will be downloadable from the project website. The initial study protocol (which will include a description of the study population, initial hypotheses to be tested, definitions of all data and covariates, discussion guides (for qualitative analyses), coding instructions for qualitative data, the survey, IRB approved informed consent documents, and the analysis plans) will be delivered in Month 9 to the PCORI organization and website. Because of the nature of CBPR, there may be changes in the protocol year 1 or even early in the second year. The complete final study protocol (which will additionally include full population and dataset descriptions, all hypotheses tested, definitions, and codebooks) will be delivered within 3 months of the end of the funding period to PCORI and made available on the project website at the same time. Thematic codes including code label and frequency of appearance in the data along with tabular materials from the quantitative analyses of the MCBS, hypotheses tested, variable definitions, statistical code instructions, and work plans will be provided to facilitate the research of other groups. A full set of these materials will be provided with the project report. The project will be registered as required by PCORI to encourage replication.

We hope policy makers and health systems will implement the Patient-Informed Surveillance Tool. Statistical analysis code with instructions will be made available facilitating policy stakeholders use of the Tool in performing population surveillance according to the National Quality Forum (NQF) 3-step healthcare quality enhancement processes. Researchers wanting to replicate or build on our quantitative findings based on the MCBS would need to obtain permission to use those data from CMS through Research Data Assistance Center (ResDAC). Contacts for doing that will be placed on the website, along with information on how to obtain our SAS code. Statistical analysis code (in SAS and/or STATA) will be linked to analysis plans.

PRINCIPAL INVESTIGATOR (LAST, FIRST, MIDDLE): [name]

## Reproduction of Research Findings (Data Sharing Plan)

*Note: The requirement for a data-sharing plan applies only to studies that are requesting funding at a level greater than \$500,000 in direct costs in any project year. The data sharing plan must:*

- *State that a complete, cleaned, de-identified copy of the final dataset used in conducting the final analyses will be made available within nine months of the end of the final year of funding.*
- *Propose a method by which investigators will make this dataset available if requested.*
- *Propose a budget that would cover costs of data sharing if requested.*

2 pages

Although a data-sharing plan is not required for a project of this size, we provide a plan because full transparency is an important objective of our work. We will include explicit descriptions of qualitative protocols and also methods for formulating, developing, and analyzing the data elements we use.

Moreover, all measures used, algorithms developed, and other results will be in the public domain. This means that individual healthcare providers or health systems will be able to apply stages to track characteristics of their treatment population and use the same sets of comparator questions to address quality and coordination, access, and PCP quality. Complete, cleaned, de-identified copies of the qualitative data used in the final analyses will be made available to other researchers within nine months of the final funding year. Outside researchers will be asked to acknowledge PCORI and publications from the project as the primary funder and source of scientific materials, respectively.

*Qualitative:* All focus group probes applied in the Second Life® (VAI and Clinician) and Urban focus groups will be downloadable from the project website. All coded thematic data will be freely available including the themes and the number of times each was identified.

*Quantitative:* Use of MCBS data requires permission from CMS and execution of a Data Use Agreement (DUA) through the CMS contractor ResDAC.

[http://www.resdac.org/cms-data/search?f%5B0%5D=im\\_field\\_privacy\\_level%3A42](http://www.resdac.org/cms-data/search?f%5B0%5D=im_field_privacy_level%3A42)

Researchers requesting quantitative data sets will be provided a set of instructions and referred to ResDAC for the completion of a formal DUA as required by Medicare for use of MCBS materials. Once a DUA is established for use of MCBS data, we will make our codebooks and analytic instructions available, facilitating full replication. Detailed variable descriptions, analytic work plans, statistician notes, and findings will be downloadable from the “Mrs. A and Mr. B” website.

PRINCIPAL INVESTIGATOR (LAST, FIRST, MIDDLE): [name]

